8 STATISTICAL CONSIDERATIONS

8.1 Sample size

Sample size has been calculated based on the primary endpoint, i.e., the prevalence of EBV infection in UC patients. In UC patients non-responders to standard of care the prevalence of EBV is expected around 50%; in UC patients responders to conventional treatment may be around 10%. We hypothesize that the prevalence of EBV infection in the control population is around 0-1%. Based on the feasibility on enrolment given study design, we plan to enroll about 100 UC patients. ~~The precision achieved with 100 patients is replicated. However, the power achieved when comparing 100 patients and 100 controls is not replicated; according to our computations is much larger than that reported by the Authors (76.9% rather than 27% with a prevalence of 10% and 99.8% rather than 87% with a prevalence of 20%).~~

Prevalence	95%CI	precision	power to detect difference from control
50%	40% - 60%	10%	100%
30%	21% - 40%	9%	100%
20%	13% - 29%	8%	99,8%
10%	5% - 18%	6%	76,9%

The power to detect a significant difference with the Fisher exact test from an expected proportion in controls of 1% is above 80% for proportions of infection of 10% or greater, considering 100 patients in each group and an alpha level of 5%. Calculations are performed using Stata 17 (StataCorp, College Station, TX, USA).

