The sample size has been calculated based on the primary endpoint, i.e., the prevalence of EBV infection in UC patients. The power to detect a significant difference with the Fisher exact test from an expected proportion in controls of 1% is above 80% for proportions of infection of 20% or greater.

This is an investigator-initiated prospective multicentre interventional without drug and medical device study evaluating the prevalence, role, life phase and the most accurate diagnostic method of EBV infection in UC as assessed by means of traditional method (*in situ* hybridization) and quantitative RealTime-PCR assay. A longitudinal study is included to assess whether EBV infection has an impact on patients' outcome. The study duration is three years.

**Study design and study
duration**

Objectives and end-points

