8.2 Analysis

Data will be described with the mean and standard deviation or the median and 25th-75th percentiles if continuous and as counts and percent if categorical. For the primary endpoint we will compute the prevalence as the ratio of the number of patients diagnosed with EBV infection to the number of patients evaluated, together with its 95%CI. We will use the Fisher exact test to compare the prevalence in UC patients to that of control. We will report the mean difference in proportions and its 95%CI. We will use binomial regression models with identity link (command binreg in Stata), to adjust for potential confounders, such as, but not limited to, age, gender, duration of disease and treatment. We will apply the 1:10 rule to adapt the number of confounders evaluated to the sample size. We will compare the prevalence of EBV infection between UC subgroups with the Fisher exact test (EP2a). In these cases, given in particular that the ratio of responders to non-responders is at yet unknown, we will compute *a posteriori* the power for the comparison. We will compute

sensitivity, specificity, area under the ROC curve and predictive values with 95% CIs for EP2b and EP2c. We will use the Spearman R and the Fisher exact test to assess the association, for continuous and categorical independent variables, respectively, with the dependent variables of EP2d to EP2h. All estimates will be presented with their 95% CI.

We will use Cox regression to assess the association of EBV infection with colectomy and of hospitalization for any cause; we will use Poisson regression to assess the association of EBV infection with the number of hospitalization from any cause. For secondary endpoints assessing associations, we will also fit regression models to adjust for possible confounders (as for the EP1) and report adjusted mean differences in proportions and 95% CI. We may also use propensity score inverse probability weights to account for the bias by indication when assessing treatment effect on the outcome.

The exploratory endpoints will be only descriptive.

We will use Stata 17 or later versions for computations. A 2-sided p-value <0.05 will be considered statistically significant. We will apply the Bonferroni correction for post-hoc comparisons.

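### Section 8.1 states power above 80% at a UC prevalence of 10%, but its own table gives 76.9%, and recalculation confirms the table

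*Protocol*

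**What the plan says.** Protocol Section 8.1 plans about 100 UC patients, a number set by feasibility of enrolment, and 100 controls. A table gives the expected precision and the power against controls for four UC prevalences:

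| UC prevalence | Power in the table |
|---|---|
| 50% | 100% |
| 30% | 100% |
| 20% | 99.8% |
| 10% | 76.9% |

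The sentence under the table takes a control prevalence of 1% and says that the Fisher test's power "is above 80% for proportions of infection of 10% or greater, considering 100 patients in each group and an alpha level of 5"%. The Summary (Section 1) makes the same claim with a different threshold: power "is above 80% for proportions of infection of 20% or greater".

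Section 8.2 fixes the test and the level: "We will use the Fisher exact test to compare the prevalence in UC patients to that of control", and "A 2-sided p-value <0.05 will be considered statistically significant".

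**The concern.** The table and the sentence beneath it describe the same test, control rate, group size and alpha. At a prevalence of 10% one gives 76.9% and the other more than 80%, so they cannot both be right. The Summary adds a second threshold for the same claim.

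Section 8.1 says the sample size rests on the primary endpoint. An ethics committee or reader who relies on the sentence would believe that the primary comparison has more than 80% power over the whole tabulated range, including its lowest row. The question is which figure is wrong and by how much.

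**Working it through.** **Inputs.** UC and control groups of 100 each, control prevalence 1%, alpha 5% (Section 8.1); Fisher exact test, two-sided (Section 8.2); UC prevalence p = 10% and upwards (Section 8.1).

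**Formula.** With X positives among 100 UC patients and Y positives among 100 controls,

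Power = Σ over y of P(Y = y) × P(X ≥ c(y)), where Y ~ Bin(100, 0.01), X ~ Bin(100, p), and c(y) is the smallest UC count for which the two-sided Fisher p-value is below 0.05. Rejections in the opposite direction contribute nothing visible.

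**Reproducing the table at p = 10%.**

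| y | P(Y = y) | c(y) | Fisher p at c(y) | Fisher p at c(y) − 1 | P(X ≥ c(y)) | Product |
|---|---|---|---|---|---|---|
| 0 | 0.3660 | 6 | 0.029 | 0.059 | 0.9424 | 0.3450 |
| 1 | 0.3697 | 8 | 0.035 | 0.065 | 0.7939 | 0.2935 |
| 2 | 0.1849 | 10 | 0.033 | 0.058 | 0.5487 | 0.1014 |
| 3 | 0.0610 | 11 | 0.049 | 0.082 | 0.4168 | 0.0254 |
| 4 | 0.0149 | 13 | 0.040 | 0.065 | 0.1982 | 0.0030 |
| 5 | 0.0029 | 15 | 0.032 | 0.051 | 0.0726 | 0.0002 |

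The products sum to 0.7685; the remaining control counts bring the total to 0.7686. That is the 76.9% in the table.

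**Other prevalences, same method.**

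| UC prevalence | Power |
|---|---|
| 10% | 76.9% |
| 10.4% | 79.9% |
| 10.5% | 80.7% |
| 11% | 84.0% |
| 12% | 89.3% |
| 20% | 99.8% |
| 30%, 50% | over 99.99% |

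All four table entries reproduce. Power crosses 80% at about 10.5%. To exceed 80% at exactly 10% would take about 106 per group (80.3%; 105 gives 79.8%).

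**Can another reading rescue the sentence?** At 10% with 100 per group:

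| Variant | Power at 10% | Stated input it departs from |
|---|---|---|
| One-sided Fisher | 84.8% | two-sided level (Section 8.2) |
| Control prevalence 0% | 94.2% | 1% in the sentence itself |
| Normal approximation, pooled variance | 80.2% | Fisher test |
| Normal approximation, unpooled variance | 81.3% | Fisher test |
| Normal approximation, continuity-corrected | 70.3% | Fisher test |

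Every variant above 80% drops an input that the protocol states.

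**Where the whole cohort is likely to lie.** Section 8.1 expects about 10% in responders and about 50% in non-responders. With a share w of non-responders and the rest responders, the pooled prevalence is 10% + 40% × w. At w = 2% this is 10.8%, with power 82.7%. Reaching 10.5% needs w = 0.5/40 = 1.25%.

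**The case against.** The strongest case on the other side is that this is a slip in one sentence with little consequence. The correct figure stands directly above it. The number of UC patients was set by feasibility, and no test, estimate or decision rule depends on the sentence. The primary comparison uses the whole UC cohort, which includes non-responders by design, so on the protocol's own expectations the pooled prevalence should exceed 10% and power should exceed 80%. All of this stands, and it limits the size of the point. It does not make the sentence true, and the protocol gives no expected prevalence for newly diagnosed patients, so a pooled value near 10% cannot be excluded.

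It might also be said that Section 8.1 hypothesises that "the prevalence of EBV infection in the control population is around 0-1"%, so that a control rate below 1% would lift power. That is correct (94.2% at 0%), but the sentence fixes 1%.

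Four stronger readings are tempting, and the protocol does not support them:

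- A reader might infer that the Summary says 80% power is reached only from 20%. It says power is above 80% at 20% or greater, which is true (99.8%) though conservative.
- A reader might infer that the plan's only power statement is wrong. There are three: the table, the sentence and the Summary. Only the sentence is wrong.
- A reader might take 10% as the protocol's expectation for the UC cohort. It is the expectation for responders.
- A reader might apply the 10% drop-out in Section 10 and compute power for 90 against 90 (70.0% at 10% prevalence). The primary endpoint is a prevalence measured on baseline samples, Section 9 replaces patients whose mucosal specimens are unavailable, and IBS controls have no follow-up visits (Appendix 4). Drop-out during follow-up does not shrink this comparison.

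Finally, 76.9% also appears in struck-through text in Section 8.1. The point does not rest on that text; the table and the sentence are both current.

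**Conclusion.** The Section 8.1 sentence is wrong as written. Under the stated test, control rate, group size and alpha, power at a UC prevalence of 10% is 76.9%, about 3 percentage points below the 80% it claims to exceed. The threshold it should carry is about 10.5%.

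The error matters only if prevalence in the whole UC cohort is about 10%. The table, the sample size and the planned analysis are unaffected, and the design is not shown to be underpowered for the prevalence the protocol expects in a mixed cohort. The conclusion assumes independent binomial counts in the two groups and the two-sided level of Section 8.2; it needs no outside figure.

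**What to change.** Replace the Section 8.1 sentence with: *Power is 76.9% at a UC prevalence of 10% and exceeds 80% from about 10.5% (control 1%, 100 per group, two-sided Fisher exact test, alpha 5%).* Use the same wording in the Summary, so that both places agree with the table.

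At minimum, change the Section 8.1 threshold from 10% to 20%, which brings it into line with its table and the Summary.

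The cost is one sentence in one or two places. No patients, procedures or analyses change. The only downside is that the stated power at 10% becomes slightly less favourable.

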8.2 Analysis

Data will be described with the mean and standard deviation or the median and 25th-75th percentiles if continuous and as counts and percent if categorical. For the primary endpoint we will compute the prevalence as the ratio of the number of patients diagnosed with EBV infection to the number of patients evaluated, together with its 95%CI. We will use the Fisher exact test to compare the prevalence in UC patients to that of control. We will report the mean difference in proportions and its 95%CI. We will use binomial regression models with identity link (command binreg in Stata), to adjust for potential confounders, such as, but not limited to, age, gender, duration of disease and treatment. We will apply the 1:10 rule to adapt the number of confounders evaluated to the sample size. We will compare the prevalence of EBV infection between UC subgroups with the Fisher exact test (EP2a). In these cases, given in particular that the ratio of responders to non-responders is at yet unknown, we will compute *a posteriori* the power for the comparison. We will compute

sensitivity, specificity, area under the ROC curve and predictive values with 95% CIs for EP2b and EP2c. We will use the Spearman R and the Fisher exact test to assess the association, for continuous and categorical independent variables, respectively, with the dependent variables of EP2d to EP2h. All estimates will be presented with their 95% CI.

We will use Cox regression to assess the association of EBV infection with colectomy and of hospitalization for any cause; we will use Poisson regression to assess the association of EBV infection with the number of hospitalization from any cause. For secondary endpoints assessing associations, we will also fit regression models to adjust for possible confounders (as for the EP1) and report adjusted mean differences in proportions and 95% CI. We may also use propensity score inverse probability weights to account for the bias by indication when assessing treatment effect on the outcome.

The exploratory endpoints will be only descriptive.

We will use Stata 17 or later versions for computations. A 2-sided p-value <0.05 will be considered statistically significant. We will apply the Bonferroni correction for post-hoc comparisons.

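### The 1:10 rule for confounders is tied to sample size, but the adjusted EBV, colectomy and hospitalisation models are limited by the number of events

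*Protocol*

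**What the plan says.** Section 8.2 (Analysis) compares EBV prevalence between UC patients and controls with the Fisher exact test, then adds adjusted models: "We will use binomial regression models with identity link (command binreg in Stata), to adjust for potential confounders". The confounder list is open: "such as, but not limited to, age, gender, duration of disease and treatment". The only limit the section places on it is "We will apply the 1:10 rule to adapt the number of confounders evaluated to the sample size".

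For the secondary endpoints that assess associations, Section 8.2 carries the approach over: "we will also fit regression models to adjust for possible confounders (as for the EP1"). It plans Cox regression for colectomy and for hospitalisation, and Poisson regression for the number of hospitalisations. No expected event counts are given for these.

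Section 8.1 (Sample size) supplies what is needed to count EBV-positive subjects: "we plan to enroll about 100 UC patients", a prevalence table running from 10% to 50%, and "We hypothesize that the prevalence of EBV infection in the control population is around 0-1" per cent.

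**The concern.** The usual guide for binary and time-to-event models is one model term per ten events, where for a binary outcome the events are the smaller of the two outcome classes. Uninfected subjects, or patients without a colectomy, add little once the other class is small. Section 8.2 names sample size as the quantity to which the number of confounders is adapted. With an outcome present in a minority of subjects, that is a much looser limit than one based on events.

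What is at stake is the adjusted differences in proportions and their confidence intervals. These are the results that would show whether an EBV association survives adjustment for age, treatment and the rest. With too many terms for the events, an identity-link binomial model can fail to converge, produce fitted probabilities outside 0 to 1, and give intervals that cover the true value too seldom.

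**Working it through.** **1. Confirm the inputs.** Section 8.1 bases its power on "considering 100 patients in each group and an alpha level of 5" per cent with the Fisher exact test, and Section 8.2 adds: "A 2-sided p-value <0.05 will be considered statistically significant". Enumerating Binomial(100, p) against Binomial(100, 0.01) gives power of 100%, 100%, 99.84% and 76.86% at p = 50%, 30%, 20% and 10%. The protocol's table has 100%, 100%, 99.8% and 76.9%. It reproduces, so 100 per group and a control prevalence of 1% are the right inputs.

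**2. Range of overall UC prevalence.** Section 8.1 expects about 50% in non-responders and 10% in responders, and Section 8.2 says their ratio is unknown. With non-responder share w, prevalence = 0.5w + 0.1(1 - w): 10% at w = 0, 20% at w = 0.25, 30% at w = 0.5, 50% at w = 1. Every row of the protocol's table is therefore possible. No separate figure is given for newly diagnosed patients.

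**3. Terms supported and terms allowed.** Events = 100 × UC prevalence, plus 0-1 infected controls. EBV-positive subjects are never the larger class (at most 51 of 200, or 50 of 100), so terms supported = events / 10. The literal rule gives 100/10 = 10 within UC and 200/10 = 20 for UC plus controls.

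| UC prevalence | EBV-positive, UC only | EBV-positive, UC plus controls | Terms supported | Left for confounders after the exposure | Literal rule, UC only | Literal rule, UC plus controls |
|---|---|---|---|---|---|---|
| 10% | 10 | 10-11 | 1 | 0 | 10 | 20 |
| 20% | 20 | 20-21 | 2 | 1 | 10 | 20 |
| 30% | 30 | 30-31 | 3 | 2 | 10 | 20 |
| 50% | 50 | 50-51 | 5 | 4 | 10 | 20 |

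The two readings differ by 20/5 = 4-fold to 20/1 = 20-fold in the UC-control model, and by 10/5 = 2-fold to 10/1 = 10-fold within UC. Using the full literal allowance would leave 10/10 = 1 to 50/10 = 5 events per confounder term within UC, and 10/20 = 0.5 to 51/20 = 2.6 in the UC-control model.

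**4. The named confounders alone.** Four confounders at one term each, plus the group term, make 5 terms and need about 50 events. That is reached only near 50% UC prevalence. At 10-30% the same model has 10/5 = 2 to 31/5 = 6 events per term.

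**5. Effect in the planned model.** Simulation of identity-link binomial regression with n = 100, 40% exposed, risks set by an odds ratio of 3 (true risk difference 0.100 at 10% prevalence, 0.178 at 20%) and independent noise covariates. The exposure share and effect size are assumptions.

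- With ten covariates, 95% interval coverage was about 63%, 82% and 91% at 10%, 20% and 30% prevalence. A separate run of 400 datasets gave about 65% and 79% at the first two, so read these to within a few percentage points.
- With one or two covariates, coverage was about 89-94%.
- With ten covariates, 12-20% of fits failed or were out of range. This share depends on the criterion: if every subject's linear predictor must lie between 0 and 1, most of the ten-covariate fits are flagged.
- With ten covariates, the median risk difference was 0.068 against 0.100 at 10% prevalence and 0.162 against 0.178 at 20%. Estimates were pulled towards zero, not away from it.

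**The case against.** The 1:10 rule is the common name for one variable per ten events, and Section 8.2 never says ten patients. The statistician may mean events and use sample size loosely. This stands: the literal reading is one of two, and the protocol does not state that 10 or 20 confounders may be used. But the sentence names only sample size, and readings that differ up to 20-fold should not be left open.

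The rule is also a ceiling, not a plan. Four confounders are named. In the UC-control model, centre, sex and age class are matched (Section 7.1), disease duration has no value in controls, and Section 6 bars controls from steroids, immunosuppressants and biologics. Twenty terms there is unrealistic, and a full covariate list may sit in a statistical analysis plan. This stands too. About ten terms within UC is less remote. Section 5.2.2 classes steroid, immunosuppressive and biological therapy at three levels each, which is 3 × 2 = 6 terms. With age, gender and duration that is 9, and with an exposure 10.

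Part of the poor coverage comes from the identity link at low prevalence, since coverage is already near 89% there with one or two covariates. This is correct, and the added covariates account for the rest of the fall.

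A reader might go further and infer that every adjusted model will be overfitted, or that associations will be exaggerated. The documents support neither. A model for a continuous outcome such as viral load may be limited by n. Inflated odds ratios belong to logistic regression, which Section 8.2 does not plan for these endpoints.

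**Conclusion.** The point holds as a wrong or at best ambiguous denominator in a rule that the protocol itself fixes. On the protocol's prevalences, events support roughly 1-5 terms including the exposure, against 10-20 confounder terms on the literal reading. If that allowance were used within UC, intervals in the planned model would be clearly too narrow at 10-20% prevalence and many fits unusable. The coverage figures rest on independent noise covariates and the assumed exposure share and effect. The event counts rest only on Section 8.1.

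The same principle applies to the Cox models for colectomy and hospitalisation, but the protocol gives no event counts there, so no size can be put on it.

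It would be wrong to conclude that the primary result is at risk. The primary comparison and the comparison of UC subgroups (endpoint a in Section 5.2.2) are unadjusted Fisher tests that this rule does not touch. Nor does the propensity weighting mentioned in Section 8.2 resolve the matter. It is foreseen for treatment effects, and a propensity model with EBV as exposure would itself be limited by the number of EBV-positive subjects. The change should be made, because the adjusted results are exposed and the correction is small.

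**What to change.** Replace the sentence in Section 8.2 with:

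> The number of model terms, including the exposure, will not exceed one per 10 events (the smaller of EBV-positive and EBV-negative subjects for binary outcomes; observed events for Cox models), with confounders entered in a pre-specified priority order.

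The priority order can be given in the protocol or in the statistical analysis plan, but before the data are seen. Models for continuous outcomes can keep a limit based on n, if the text says so.

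If the authors already meant events, the edit changes nothing in practice. If not, the cost is real: at about 10% UC prevalence almost no confounder can be entered, and at 20% only one. Adjusted results in that range would have to be reported as exploratory, with residual confounding acknowledged. No extra patients, visits or data are needed.

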5.2.2 Secondary endpoint

a- Comparison of the presence of EBV infection in the cohort of patients suffering from UC and divided into the following subgroups: a) new diagnosis; b) responders to conventional therapies; c) non-responders to conventional therapies, in order to unravel whether it is a bystander or causative of the onset/relapse of the disease and whether it is responsible for refractoriness to standard of care.

b- Evaluation of the diagnostic ability in detection of EBV infection of ISH performed on mucosal specimens with respect to qRealTime-PCR.

c- Evaluation of the diagnostic ability in detection of EBV infection between qRealTime-PCR performed on peripheral blood samples with respect to mucosal specimens.

d- Evaluation of association between mucosal/blood viral load and mucosal damage as endoscopically assessed (see paragraph 5).

e- Evaluation of association between clinical index of UC activity and EBV infection.

f- Evaluation of association between steroid therapy (absent, previous or current) and EBV infection.

g- Evaluation of association between immunosuppressive therapy (absent, previous or current) and EBV infection.

h- Evaluation of association between biological therapy (absent, previous or current) and EBV infection.

i- Evaluation of the prognostic role of EBV infection on the 6 and 12 months outcome (colectomy / number of hospitalization / cause of hospitalization).

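### EP2a is meant to inform on UC onset, but it compares UC subgroups only with each other; new-diagnosis UC is never tested against non-UC controls

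*Protocol*

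**What the plan says.** Protocol 5.2.2(a), repeated among the objectives in the Summary, splits the UC cohort into "a) new diagnosis; b) responders to conventional therapies; c) non-responders to conventional therapies". The comparison is made "in order to unravel whether it is a bystander or causative of the onset/relapse of the disease", and also to see whether EBV accounts for refractoriness.

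Protocol 8.2 names one test for this endpoint: "We will compare the prevalence of EBV infection between UC subgroups with the Fisher exact test (EP2a". The only planned test that involves controls is the primary one: "We will use the Fisher exact test to compare the prevalence in UC patients to that of control". It takes the UC cohort as a whole. Regression models are foreseen for confounder adjustment, but none is designated as the analysis of new diagnoses against controls.

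Protocol 8.1 supplies the expected rates. "In UC patients non-responders to standard of care the prevalence of EBV is expected around 50" per cent; "in UC patients responders to conventional treatment may be around 10" per cent; "We hypothesize that the prevalence of EBV infection in the control population is around 0-1" per cent. It gives neither a rate nor a number for new diagnoses.

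**The concern.** The purpose, the groups and the test are all written in the protocol, and for onset they do not match. The null hypothesis of EP2a is equal EBV prevalence in three groups that all have UC. A hypothesis of no association with onset would be equal prevalence in newly diagnosed UC and in people without UC. The two can differ in either direction, so neither a significant nor a non-significant EP2a bears on onset by itself.

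Treatment adds to the problem. The Background (section 3) regards therapies acting on T-cells as a potential trigger of EBV reactivation, and EP2f to EP2h study steroids, immunosuppressants and biologics as correlates of EBV. New diagnoses are the UC subgroup least exposed to these drugs, and the functional controls take none of them (section 6). The least confounded contrast for this question is therefore available in the data, yet no analysis is assigned to it.

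**Working it through.** **Inputs from the protocol.** Responders 10%, non-responders 50%, controls 1% (upper end of the stated range and the value used for power), 100 UC patients and 100 controls, two-sided alpha 0.05 (8.1, 8.2).

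**Assumed, because the protocol gives no figure.** The split of UC patients into new diagnosis / responder / non-responder, and the rate in new diagnoses.

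**Step 1: reproduce the plan's own figure.** Exact power of the two-sided Fisher test is the sum, over all pairs (i, j) with Fisher p < 0.05, of Bin(i; 100, p) × Bin(j; 100, 0.01). For p = 10%, 20%, 30% and 50% this gives 76.9%, 99.8%, 100% and 100%, matching the table in 8.1.

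**Step 2: no association at onset.** Set new diagnoses at 1%, responders at 10%, non-responders at 50%. The EP2a rejection probability sums the three binomials over all outcomes where the 3×2 Fisher (Freeman-Halton) test has p < 0.05. Pooled UC prevalence is (n_new × 0.01 + n_resp × 0.10 + n_non × 0.50)/100; for 20/40/40 it is (0.2 + 4 + 20)/100 = 24.2%. The last column is the power of the primary test (EP1) against 100 controls at 1%.

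| Split | EP2a rejects | Pooled UC | EP1 rejects |
|---|---|---|---|
| 20/40/40 | 99.9% | 24.2% | >99.9% |
| 33/33/34 | 99.97% | 20.6% | >99.9% |
| 20/50/30 | 99.8% | 20.2% | 99.9% |
| 10/60/30 | 98.8% | 21.1% | >99.9% |
| 20/60/20 | 98.4% | 16.2% | 99.1% |
| 30/50/20 | 99.5% | 15.3% | 98.6% |

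Both tests are almost surely significant although new diagnoses look exactly like controls.

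**Step 3: read pairwise instead, at 0.05/3.** In the same scenario and splits:
- responders against non-responders rejects in 85-96%;
- new diagnoses against non-responders rejects in 77-99.9%;
- new diagnoses against responders rejects in 0-3%.

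Every pair is UC against UC, so none supplies the missing reference.

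**Step 4: EBV equally raised in all UC.** Set all three subgroups to 20% or 30%, with controls at 1%. EP2a rejects in 4.6-4.9% over the same splits, that is, at about its nominal level. Only the pooled primary test, with power 99.8% or more (step 1), hints that new diagnoses are affected.

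**Step 5: the missing comparison.** Two-sided Fisher test, new diagnoses against 100 controls at 1%:

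| New diagnoses | true rate 1% | 10% | 20% | 30% |
|---|---|---|---|---|
| 10 | 0.4% | 25% | 60% | 83% |
| 20 | 0.7% | 41% | 83% | 97% |
| 33 | 0.3% | 58% | 95% | 99.7% |

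**Step 6: room for adjustment.** With 20 new diagnoses at 20% and 100 controls at 1%, expected positives are 20 × 0.20 + 100 × 0.01 = 5. Read as one covariate per ten events, the protocol's 1:10 rule allows 5/10 = 0.5, so no covariate.

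**The case against.** A reader might infer that EP2a will give the wrong answer about onset in both directions. The protocol does not support that. It contains no rule that reads a significant EP2a as a role in onset or a non-significant one as bystander. Three further points stand.

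- Rejection driven by 50% against 10% is a correct and wanted signal for refractoriness, which is part of the purpose of EP2a.
- In the equal-prevalence case, a flat EP2a beside a strongly positive primary result would suggest that EBV is raised throughout UC. In the no-onset case, section 8.2 asks for all estimates with confidence intervals, so a low rate in new diagnoses would be visible, and no significant pairwise result would be expected to show new diagnoses higher.
- Section 8.2 does not say whether the Fisher test is three-group or pairwise, and the 98-100% applies literally only to the former.

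It can also be argued that the adjusted primary model covers the gap. Section 8.2 lists disease duration and treatment as possible confounders; with controls coded zero on both, the UC coefficient approximates untreated, new UC minus control. That depends on the model form. In the no-onset scenario there are about 15.3 + 1 = 16 to 24.2 + 1 = 25 positives, which leaves one or two covariates under the 1:10 rule. Nothing designates this model as the onset analysis.

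Nor does the protocol say that treatments do reactivate EBV; it calls them a potential trigger. What remains is that a stated purpose of EP2a has no test with a non-UC reference.

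**Conclusion.** The point holds in this form: the test assigned to EP2a cannot address onset because it lacks a non-UC reference, and the primary test does not fill the gap because it pools new diagnoses with treated patients. EP2a rejects in about 98-100% of trials when new diagnoses equal controls, and in about 5% when all UC subgroups are equally raised.

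These figures rest on the protocol's 10%, 50% and 1%, on assumed splits, and on an assumed rate in new diagnoses; the 1% is borrowed from the controls. The direction of the conclusion does not depend on the split within the range tried. The defect concerns one purpose of a secondary endpoint. The responder against non-responder contrast remains sound for refractoriness, and the primary endpoint is unaffected. It should be corrected, since onset is a stated aim and the data needed are already being collected.

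**What to change.** In 5.2.2(a) and 8.2 (and the matching text in the Summary):

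- Keep the between-subgroup comparison and assign it to refractoriness. State that no conclusion on onset is drawn from it.
- Add a comparison of new-diagnosis UC with the functional (C1-C4) controls: difference in proportions with an exact 95% CI, and a Fisher test. Make the unadjusted result the main one, and adjust for covariates only as far as the 1:10 rule allows.
- Report EBV prevalence in the 20 microscopic-colitis patients descriptively alongside, as the inflamed non-UC reference.
- Limit the wording to association with EBV at diagnosis. The comparison is cross-sectional; it cannot establish that EBV causes onset, nor exclude that inflammation itself raises EBV.

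The cost is one more comparison on data already collected, plus the wording. The interval will be wide if new diagnoses are few, and power at 20% prevalence falls to 60% with only 10. The controls were matched to the UC cohort as a whole, so the new-diagnosis subset may differ from them in age, sex or centre; that should be described.
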